7.4 Criteria for Withdrawal / Discontinuation of Participants

Subjects may voluntarily withdraw from study participation at any time without having to provide a reason. Subjects may be withdrawn because of the appearance of a new health condition requiring care or medications prohibited by the protocol, unacceptable adverse event, refusal to continue treatment, or at the Investigator's discretion if it is in the subject's best interest.

A subject who withdraws informed consent before randomization or who develops a violation of the selection criteria before randomization is defined as a screening failure. No follow-up of screening failures will be performed.

Participants who withdraw informed consent, who do not fulfil inclusion/exclusion criteria after obtaining informed consent or who are diagnosed with an alternative disease (e.g. influenza infection) AND have not received any study medication will be withdrawn from the study.

Participants who experience a type I allergic reaction after any dose of study medication will be discontinued from further study interventions. Withdrawn or discontinued participants will not be replaced. Follow-up for all patient groups will be explained in [Section 8.5](#).

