8.5 Data Collection and Follow-up for Withdrawn Participants

Patients can leave the study at any time for any reason if they wish to do so without any consequences. The Investigator can decide to withdraw a patient from the study for medical reasons. A patient who experiences a treatment-emergent anaphylactic reaction will not be permitted to receive further treatment with rhC1INH.

Patients who withdraw informed consent will not be followed up. Although incomplete, data and samples collected up to the discontinuation will be analyzed. Personal data, samples and the confidentiality of these patients will be managed according to the same standards as per other evaluated completed patients.

Patients who are withdrawn from the study because they did not receive any study medication will not be followed up. Patients who are withdrawn because SARS-CoV-2 infection was not confirmed will be followed only for safety assessments.

Patients who are discontinued from the study because of a type I allergic reaction during the treatment phase are followed in the same fashion as planned for all participants.

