9.1.5 Assessments in Participants Who Prematurely Stop the Study

Patients who are withdrawn from the study will remain in the trial for the purpose of follow-up and data analysis and will be followed as planned with the following exceptions:

- Patients, who withdraw consent for all study measures, will be asked to have assessments performed as appropriate for the final 4 week study visit (*i.e.* a structured telephone interview). The same approach applies for all active study participants if the trial is stopped early. Patients who withdraw consent are at liberty to refuse any or all individual components of the final assessment.
- Patients who are withdrawn because they have not received any study medication will not be followed up and will not receive a final study assessment.
- Patients who discontinue the study because of safety concerns will be followed as planned.
- Patient with a type I allergic reaction will be referred to an allergist associated with the site for further work-up.

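### Withdrawal without follow-up hinges on not having received study medication, which is always true in SOC but true for rhC1INH patients only until the first dose, so loss of the Day-7 score can differ by arm

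*Protocol*

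**What the plan says.** Protocol 7.4 first classes consent withdrawals and selection-criteria violations that arise before randomisation as screening failures. It then deals with participants who withdraw consent, who prove after consent not to meet the criteria, or who turn out to have another disease. That rule ends: "AND have not received any study medication will be withdrawn from the study". SAP 5.7 repeats it and refers to Protocol 8.5 for follow-up.

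Follow-up is then set in two places.

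- **Protocol 8.5:** "Patients who are withdrawn from the study because they did not receive any study medication will not be followed up". The next sentence reads: "Patients who are withdrawn because SARS-CoV-2 infection was not confirmed will be followed only for safety assessments". On consent: "Patients who withdraw informed consent will not be followed up".
- **Protocol 9.1.5** opens with a general rule, "Patients who are withdrawn from the study will remain in the trial for the purpose of follow-up and data analysis", and lists exceptions. One is: "Patients who are withdrawn because they have not received any study medication will not be followed up and will not receive a final study assessment". Another is that patients who withdraw consent for all study measures "will be asked to have assessments performed as appropriate for the final 4 week study visit".

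Protocol 8.1.1 and the flow-chart notes in 9.1 use the term study medication for rhC1INH. Protocol 8.1.2 and 8.2.2 give the control arm SOC only. The FAS/ITT set contains every randomised patient in the allocated arm (Protocol 11.4.1, SAP 14.2). A missing Day-7 score is filled by LOCF (Protocol 11.5, SAP 14.9), and withdrawn patients are not replaced.

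**The concern.** A rule that ends data collection after randomisation should not depend on something that only one arm can receive. Here the same late finding, such as an exclusion criterion that was missed or an influenza diagnosis, can end follow-up for a control patient while a dosed rhC1INH patient with that finding stays in.

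Allocation is open (Protocol 6.2.2), so staff know the arm when they make the finding. The patient still counts in the primary analysis, but with an early in-hospital score in place of the Day-7 score. Loss that differs by arm and relates to diagnosis is the kind that randomisation does not protect against. The planned mean and multiple imputation cannot recover outcomes that were never collected.

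**Working it through.** **1. When the rule operates.** Pre-randomisation cases are already screening failures, so the rule has its effect after randomisation. The flow-chart note on virology in Protocol 9.1 gives a route: it allows inclusion on symptoms and radiology with the PCR to follow. The note on dosing foresees PCR results that do not confirm COVID-19.

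**2. Who meets the condition.**

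| Late finding in | No study medication received? | Result under 7.4 |
|---|---|---|
| SOC patient, any day | Always true | Withdrawn |
| rhC1INH patient, not yet dosed | True | Withdrawn |
| rhC1INH patient, dosed | False | Not withdrawn by this rule |

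The Synopsis places the first dose on Day 0, the day of randomisation, so the second row is a short window.

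**3. Who then loses the Day-7 score.** There are two readings of the no-follow-up sentences in 8.5 and 9.1.5.
- If they cover anyone withdrawn without study medication, the loss falls mainly in SOC.
- If they cover only patients for whom non-receipt is itself the reason for withdrawal, they describe rhC1INH patients who were never dosed, and the loss falls in that arm.

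The loss depends on arm under both readings.

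**4. Unconfirmed infection.** Protocol 8.5 gives safety-only follow-up and names no arm. On its face this drops the Day-7 efficacy score in either arm. It conflicts with 7.4, which does not withdraw a dosed patient on this ground, and with the no-follow-up sentences for an undosed one.

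**5. The plan's own figures.** With δ = 1, σ = 1.5, two-sided α = 0.05 and power 0.80, n per group = 2σ²(1.960 + 0.842)²/δ² = 2 × 2.25 × 7.85 = 35.3, so 36 (37 with the t distribution), against 38 stated. For the total, 92 × 9/8 for 2:1 allocation × 1.165 for three Pocock stages = 120.6, against 120 stated. The 1-point target and the 80 + 40 split are therefore fair yardsticks.

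**6. Size of the bias.** Shift in an arm's mean = f × (carried score − true Day-7 score), where f is the fraction of the arm affected. The documents give neither quantity; both are assumptions. In SOC, f of 5–10% means 2–4 of 40 patients.

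| f | Gap 1.5 points | Gap 2 points |
|---|---|---|
| 5% | 0.05 × 1.5 = 0.075 | 0.05 × 2 = 0.10 |
| 10% | 0.10 × 1.5 = 0.15 | 0.10 × 2 = 0.20 |

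This is 7.5–20% of the 1-point target. An inpatient scores at least 3 and a discharged patient 1 or 2, so a patient who would have gone home by Day 7 is scored too high. The SOC mean rises, which favours rhC1INH. If the affected patients worsen, the gap is negative and the sign reverses. If the loss falls in the rhC1INH arm, the same formula moves that arm's mean instead.

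**7. Effect on the test.** A simulation under no treatment effect (80 vs 40, one unstratified Wilcoxon look at 0.05, 20,000 runs, SOC-only loss, carried score fixed at 4, affected patients assumed to recover quickly) gave type I error of 7.0% at 5% loss and 12.5% at 10%, against about 5% with complete follow-up. The assumed Day-7 mean of affected patients was 0.40 × 1 + 0.40 × 2 + 0.15 × 3 + 0.05 × 4 = 1.85. The gap was thus 2.15 points, slightly above the range in step 6.

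**8. Power.** If 5% or 10% of SOC scores were simply absent (38 or 36 controls), fixed-design power for 1 point falls from 93.1% to 92.3% or 91.3%. Power is not the issue.

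**The case against.** A reader might infer that Day-7 data are lost from the SOC arm alone and that the bias must favour rhC1INH. The documents do not support that, for these reasons.

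- **Reason for withdrawal.** The no-follow-up sentences speak of patients withdrawn because they had no study medication. A control patient with another diagnosis is withdrawn because of the diagnosis, and the general rule in 9.1.5 would then keep that patient in follow-up. This is a fair reading. It moves the loss to undosed rhC1INH patients but does not make the rule neutral between arms.
- **Safety-only follow-up.** For unconfirmed infection, the clearest route to a late change of diagnosis, 8.5 provides safety follow-up in either arm. It is therefore wrong to say that all such patients go unfollowed, or that dosed rhC1INH patients are untouched. The Day-7 efficacy score is still not provided for.
- **Scope of the AND.** It may attach only to the alternative-disease clause. Ineligible patients would then be withdrawn in both arms, but the imbalance remains for alternative diagnoses.
- **Few patients.** A positive PCR is an inclusion criterion and eligibility is checked at Visit 1, so the number may be small. A rate of 5–10% in SOC would take half or all of the planned drop-out allowance of about 10%. This stands, and it limits confidence in the size.
- **Test used.** The planned analysis is a baseline-stratified Wilcoxon test with interim looks. Neither a mean shift nor an unstratified single look is that test. This also stands; the figures are illustrations.

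The consent-withdrawal conflict is a separate matter. It names no arm, and the assessment that 9.1.5 asks for is a 4-week telephone interview, which is not a Day-7 score.

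**Conclusion.** The concern holds in a limited form. As written, withdrawal and loss of the Day-7 score after randomisation can differ by arm, because the condition rests on receipt of rhC1INH. The loss falls mainly in SOC on one reading and among undosed rhC1INH patients on the other; the text does not settle which. Because the FAS keeps these patients and LOCF supplies their score, the primary comparison can be biased.

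The size is not known. The shift of about 0.08–0.20 point in favour of rhC1INH assumes that 5–10% of SOC patients and essentially no rhC1INH patients are affected, and that the affected patients improve by 1.5–2 points. The direction is as much an assumption as the amount. The arm-dependent wording and the disagreements among 7.4, 8.5 and 9.1.5 do not depend on any rate. Should-fix, with medium confidence on size.

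**What to change.** - Collect the Day-7 and Day-14 WHO score for every randomised patient, whatever the arm, dosing status or later finding on eligibility or diagnosis, unless consent to data collection is withdrawn.
- Remove non-receipt of study medication as a ground for ending follow-up after randomisation. Any remaining post-randomisation rule should use criteria that apply equally in both arms.
- Reconcile Protocol 7.4, 8.5 and 9.1.5, and SAP 5.7. State what is recorded when infection is not confirmed, and settle whether patients who withdraw consent are approached. If they are, ask permission to record Day-7 and Day-14 status.

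The change addresses the bias under either reading of the no-follow-up sentences. It costs protocol wording and a few chart reviews or calls: the scale is already scored daily (Protocol 9.1.1), and the weekly post-discharge contacts already include it (Protocol 9.2.1, Visit 7).

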8. STUDY INTERVENTION

8.1 Identity of Investigational Products (treatment / medical device)

8.1.1 Experimental Intervention (treatment)

RhC1INH (Ruconest®) will be supplied by the production company Pharming Technologies, B.V., the Netherlands. RhC1INH is a recombinant analogue of human C1-INH for intravenous injection. The primary and secondary structures of the molecule and target protease selectivity are consistent with those of plasma-derived C1-INH. RhC1INH is purified from the milk of transgenic rabbits, and supplied as a sterile, preservative-free, white/off-white lyophilized powder for reconstitution for injection. RhC1INH contains less than 0.002% of rabbit-related impurities. One international unit (U) of rhC1INH activity is defined as the equivalent of C1-INH activity present in 1 mL of pooled normal plasma. Each vial of RhC1INH contains 2100 U of rhC1INH, 937 mg of sucrose, 83.3 mg of sodium citrate dihydrate and 1.0 mg of citric acid monohydrate. After reconstitution with 14 mL of sterile water for injection, each vial of rhC1INH contains 150 U of rhC1INH per 1 mL in a 20 mM sodium citrate buffer with a pH of 6.8. RhC1INH does not contain preservatives and each vial is for single use only. After randomization, a pharmacist will open the respective sealed boxes, will reconstitute the respective number of rhC1INH vials and prepare the study medication. RhC1INH is for intravenous use only. The reconstituted solution is administered as a slow intravenous injection over approximately five minutes. Recommended doses of rhC1INH for the treatment of an acute angioedema attack are 50 U/kg if body weight <84kg and 4200 U if >84kg. A second dose may be administered at the same recommended dose level within a 24-hour period. In this study, we will not use the product according to the licensed indication. A market batch will be used for the study.

8.1.2 Control Intervention (standard/routine/comparator treatment / medical device)

Participants in the control arm will receive SOC treatment according to local guidelines.

8.1.3 Packaging, Labelling and Supply (re-supply)

The investigational product (rhC1INH) is supplied in single-use 24ml glass vials with a stopper (siliconized chlorobutyl rubber) and a flip-off seal (aluminium and colored plastic). Each carton contains one single-use vial. Sufficient amounts of rhC1INH will be supplied by the manufacturer Pharming Technologies B.V. prior to study commencement. Both the carton and

the glass vial of rhC1INH are labelled as 'Ruconest® (C1 esterase inhibitor [recombinant]), powder for solution for injection. For intravenous infusion 2100U/vial'. One vial contains 2100 U of rhC1INH, corresponding to 2100 U/14 ml after reconstitution, or a concentration of 150 U/ml.

8.1.4 Storage Conditions

RhC1INH will be stored at 2-25°C at the pharmacy of the study sites (shelf life 48 months when stored at 2-25°C, prior to reconstitution) in a dedicated, secure and temperature-monitored study room at the in-house pharmacy which will be inaccessible to unauthorized personnel. Drug accountability will be monitored according to ICH-GCP E6 (R2) Guideline for Good Clinical Practice. More details are described in the Study Pharmacy Manual.

8.2 Administration of Experimental and Control Interventions

8.2.1 Experimental Intervention

RhC1INH (Ruconest®) will be administered at (150 U/ml) at a 50 U/kg dose (max dose of 4200 U) as a slow intravenous injection via a peripheral or central intravenous line in approximately 5 minutes every 12 hours; for 4 days. A total of 8 doses will be administered. (The licensed dosage for rhC1INH is weight-based (50 U/kg up to 84 kg and 4200 U for a bodyweight of \geq 84 kg). This is based on the aim to at least achieve a level of 0.7 U/ml C1-INH in patients with hereditary angioedema (lower limit of normal of C1-INH activity). Simulation studies have revealed that this aim is achievable with the licensed dosing⁴⁵.

However, these simulations have also shown that C1-INH levels will be lower when using 50 U/kg compared to 4200 U in patients with a bodyweight $<$ 84kg. As for the current trial the aim is not to correct underlying *absolute* C1-INH deficiency (as in case of hereditary angioedema), but to ensure that a level of at least twice the serum concentration will be achieved in the vast majority of patients, we will use the licensed dose.

In patients with normal C1-INH levels, the chosen dose will increase plasma C1-inhibitor activities by at least 100% (4200 U) respectively. To maximize efficacy rhC1INH will be administered repeatedly over 4 days. Maximal volume of the injection is 28ml (4200 U) per administration.

Repeated administration of rhC1INH was chosen for several reasons. First, hyperinflammation caused by SARS-CoV-2 is a phenomenon that may last for several days, and hence sustained inhibition of the CS and the KK system is required. Second, the elimination half-life of rhC1INH was 2.5 hours³². Third, a decline of C1-INH activity to pre-administration levels was demonstrated within four to six hours after administration of rhC1INH at a dose of 50 U/kg⁴⁶.

Duration of exposure to rhC1INH will be approximately 4 days. Participants will be followed in hospital for at least 12 hours after the last dose and via structured telephone interviews four weeks later.

8.2.2 Control Intervention

Participants in the control arm will receive SOC treatment according to local guidelines.

8.3 Dose / Device Modifications

The only modification will be omission of subsequent doses of rhC1INH if the participant develops a type 1 allergic reaction including an anaphylactic reaction after any dose of rhC1INH. If the patient is discharged or transferred to another facility the intervention will be ceased.

8.4 Compliance with Study Intervention

RhC1INH syringes for all administration time points on a given day will be prepared by the pharmacist. The study drug including the exact time for administration of the first and subsequent syringes will be entered into the electronic prescribing system/chart or added to the paper chart. As this study involves IV administration of the IMP by nurses, patient compliance measures are not necessary. IMP will be administered by a nurse according to the site's standard procedures. Two nurses will check the IMP with respect to dose, study number and patient's identity before administration to the patient. Nurses will document the syringe number and the time of administration in the electronic or paper chart.

8.5 Data Collection and Follow-up for Withdrawn Participants

Patients can leave the study at any time for any reason if they wish to do so without any consequences. The Investigator can decide to withdraw a patient from the study for medical reasons. A patient who experiences a treatment-emergent anaphylactic reaction will not be permitted to receive further treatment with rhC1INH.

Patients who withdraw informed consent will not be followed up. Although incomplete, data and samples collected up to the discontinuation will be analyzed. Personal data, samples and the confidentiality of these patients will be managed according to the same standards as per other evaluated completed patients.

Patients who are withdrawn from the study because they did not receive any study medication will not be followed up. Patients who are withdrawn because SARS-CoV-2 infection was not confirmed will be followed only for safety assessments.

Patients who are discontinued from the study because of a type I allergic reaction during the treatment phase are followed in the same fashion as planned for all participants.

8.6 Trial Specific Preventive Measures

All participants will receive standard supportive care established at the sites which may include off-label use of certain drugs that are deemed to be effective in COVID-19 (e.g. hydroxychloroquine, lopinavir/ritonavir). In addition, escalation of treatment with off-label use of certain drugs (e.g. tocilizumab) in deteriorating participants is allowed during the trial.

In terms of risk, rhC1INH, a recombinant human protein, has a very favorable side effect profile and major adverse events attributable to study medication are not expected in this study. Anaphylactic reactions are exceptionally rare and have only been observed in a single patient with a pre-existent allergy to rabbits. Although patients with rabbit allergy will be excluded from participating in the study, included subjects will be monitored for anaphylactic events during and for at least 12 hours after the last administration of rhC1INH. If patients develop type 1 allergic reactions following the administration of rhC1INH treatment according to in-house guidelines (potentially involving administration of antihistamines, corticosteroids, intravenous fluids and if needed adrenaline) will be provided.

No influence of rhC1INH on laboratory parameters or vital signs, including ECG was observed in previous clinical studies. Hence, we will not perform additional laboratory monitoring exceeding routine laboratory controls planned by the treating team (with the exception of the above-mentioned additional biomarker analyses). No interactions with other drugs are known.

If female, patients must be/have:

- Post-menopausal, defined as the absence of menses for at least one year, OR
Surgically sterile, defined as a bilateral tubal ligation at least 6 months prior to administration of study drug, bilateral oophorectomy, or complete hysterectomy, OR

- Using an effective means of contraception with a failure rate less than 1% per year (e.g. oral contraceptives, contraceptive injections, intrauterine device, double-barrier method, male partner sterilization), OR
- A negative pregnancy test before study entry/randomization. We expect the rate of female patients of childbearing age who may become pregnant to be <10% of all patients potentially eligible for this study. Due to the short treatment period (4 days) and half-life of rhC1INH (2.5 hours) an effective means of contraception is not mandatory during the hospitalization treatment phase. At least one method of contraception (oral contraceptives, barrier methods, approved contraceptive implant or abstinence) is required for the entire follow up study period
- Concomitant Interventions (treatments)

All participants will receive standard supportive care established at the sites which may include off-label use of certain drugs that are deemed to be effective in COVID-19 (e.g. hydroxychloroquine, lopinavir/ritonavir, prophylactic anticoagulation). In addition, escalation of treatment with off-label use of certain drugs (e.g. tocilizumab) in deteriorating participants is allowed during the trial. Randomization will be stratified by site to compensate for different standards of supportive care. Off-label use of drugs for the treatment of COVID-19 will be recorded in the CRF. Escalation of treatment is one outcome of interest.

Patients are allowed to use all their regular medication during the trial. In addition, patients will receive all drugs required for the treatment of COVID-19 or its consequences. The care of the participant will remain unaffected by inclusion into the study or by study group assignment.

